8.2.3.2 Unexpected Events

Unexpected events are those not listed at the observed specificity or severity in the protocol, informed consent, investigator brochure, or FDA-approved package insert. An event is considered unexpected if it is listed as occurring within the class of drugs or otherwise expected from the drug's pharmacological properties but which has not been previously observed with this specific investigational agent.

8.2.3.3 Adverse Reactions

An adverse event is considered to be an adverse reaction if there is evidence to suggest a causal relationship to the study agent. This may include a single occurrence of an event strongly associated with drug exposure (e.g. Stevens-Johnson Syndrome), one or more occurrence of an event otherwise uncommon is the study population, or an aggregate analysis of specific events occurring at greater than expected frequency.

8.2.3.4 Events of Clinical Interest

Selected non-serious and serious adverse events are also known as Events of Clinical Interest (ECI) and must be recorded as such on the Adverse Event case report forms/worksheets and reported within 24 hours of site knowledge of the event to the UC CCC Cancer Clinical Trials Office and Lead Principal Investigator and within 2 working days to Merck Global Safety. (Attn: Worldwide Product Safety; [contact]) and Sarah Cannon Development Innovation Safety Department.

Events of clinical interest for this trial include:

1. an overdose of Merck product, as defined in Section 7.2.1, that is not associated with clinical symptoms or abnormal laboratory results.

2. an elevated AST or ALT lab value that is greater than or equal to 3X the upper limit of normal and an elevated total bilirubin lab value that is greater than or equal to 2X the upper limit of normal and, at the same time, an alkaline phosphatase lab value that is less than 2X the upper limit of normal, as determined by way of protocol-specified laboratory testing or unscheduled laboratory testing.*

*Note: These criteria are based upon available regulatory guidance documents. The purpose of the criteria is to specify a threshold of abnormal hepatic tests that may require an additional evaluation for an underlying etiology.

Subjects should be assessed for possible ECIs prior to each dose. Lab results should be evaluated and subjects should be asked for signs and symptoms suggestive of an immune-related event. Subjects who develop an ECI thought to be immune-related should have additional testing to rule out other etiologic causes. If lab results or symptoms indicate a possible immune-related ECI, then additional testing should be performed to rule out other etiologic causes. If no other cause is found, then it is assumed to be immune-related.

8.2.4 Evaluating Adverse Events

An investigator will evaluate all adverse events according to the NCI Common Terminology for Adverse Events (CTCAE), version 5. Any adverse event which changes CTCAE grade over the course of a given episode will have each change of grade recorded on the adverse event case report forms/worksheets.

All adverse events regardless of CTCAE grade must also be evaluated for seriousness.

Protocol Version: 04/10/2019

Page 49 of 72

Table 6 Evaluating Adverse Events

An investigator, will evaluate all adverse events as to:

v5 CTCAE Grading	Grade 1	Mild; asymptomatic or mid symptoms; clinical or diagnostic observations only; intervention not indicated.	
	Grade 2	Moderate; minimal, local or noninvasive intervention indicated; limiting age-appropriate instrumental ADL.	
	Grade 3	Severe or medically significant but not immediately life-threatening; hospitalization or prolongation or hospitalization indicated; disabling; limiting self-care ADL.	
	Grade 4	Life threatening consequences; urgent intervention indicated.	
	Grade 5	Death related to AE	
Seriousness	A serious adv	verse event is any adverse event occurring at any dose or during any use of Merck product that:	
	†Results in d	leath; or	
	† Is life threatening; or places the subject, in the view of the investigator, at immediate risk of death from the event as it occurred (Note: This does not include an adverse event that, had it occurred in a more severe form, might have caused death.); or		
	†Results in a persistent or significant disability/incapacity (substantial disruption of one's ability to conduct normal life functions); or †Results in or prolongs an existing inpatient hospitalization (hospitalization is defined as an inpatient admission, regardless of length of stay, even is hospitalization is a precautionary measure for continued observation. (Note: Hospitalization for an elective procedure to treat a pre-existing condition that not worsened is not a serious adverse event. A pre-existing condition is a clinical condition that is diagnosed prior to the use of a Merck product an documented in the patient's medical history.); or		
	†Is a congeni	ital anomaly/birth defect (in offspring of subject taking the product regardless of time to diagnosis);or	
	Is a new cancer (that is not a condition of the study) (although not serious per ICH definition, is reportable to the Lead Principal Investigator within of site knowledge of the event and to Merck and Sarah Cannon Development Innovation Safety Department within 2 working days to meet ce requirements); or		
	purposes. An	se (whether accidental or intentional). Any adverse event associated with an overdose is considered a serious adverse event for collection overdose that is not associated with an adverse event is considered a non-serious event of clinical interest and must be reported within 24 hours edge of the event to the Lead Principal Investigator and to Merck and Sarah Cannon Development Innovation Safety Department within 2.	

Protocol Version: 04/10/2019 Page 50 of 72

	Other important medical events that may not result in death, not be life threatening, or not require hospitalization may be considered a serious adverse event when, based upon appropriate medical judgment, the event may jeopardize the subject and may require medical or surgical intervention to prevent one of the outcomes listed previously (designated above by a †).	
Duration	Record the start	and stop dates of the adverse event. If less than 1 day, indicate the appropriate length of time and units
Action taken	Did the adverse	event cause study agent(s) to be discontinued?
Relationship to Merck or Evelo Product		
	Exposure Is there evidence that the subject was actually exposed to study agent(s) such as: reliable history, acceptable compliance assessment (procunt, diary, etc.), expected pharmacologic effect, or measurement of drug/metabolite in bodily specimen?	
	Time Course	Did the AE follow in a reasonable temporal sequence from administration of study agent(s)? Is the time of onset of the AE compatible with a drug-induced effect (applies to trials with investigational medicinal product)?
	Likely Cause	Is the AE not reasonably explained by another etiology such as underlying disease, other drug(s)/vaccine(s), or other host or environmental factors

Protocol Version: 04/10/2019 Page 51 of 72

Relationship	The following components are to be used to assess the relationship between the study agent(s) and the AE: (continued)		
to Merck or Evelo Product	Dechallenge	Was study agent(s) discontinued or dose/exposure/frequency reduced?	
(continued)		If yes, did the AE resolve or improve?	
(continued)		If yes, this is a positive dechallenge. If no, this is a negative dechallenge.	
		(Note: This criterion is not applicable if: (1) the AE resulted in death or permanent disability; (2) the AE resolved/improved despite continuation of pembrolizumab; or (3) the trial is a single-dose drug trial); or (4) pembrolizumab is only used one time.)	
	Rechallenge	Was the subject re-exposed to study agent(s) in this study?	
		If yes, did the AE recur or worsen?	
		If yes, this is a positive rechallenge. If no, this is a negative rechallenge.	
		(Note: This criterion is not applicable if: (1) the initial AE resulted in death or permanent disability, or (2) the trial is a single-dose drug trial); or (3) pembrolizumab is only used one time).	
		NOTE: IF A RECHALLENGE IS PLANNED FOR AN ADVERSE EVENT WHICH WAS SERIOUS AND WHICH MAY HAVE BEEN CAUSED BY STUDY AGENT(S), OR IF REEXPOSURE TO STUDY AGENT(S) POSES ADDITIONAL POTENTIAL SIGNIFICANT RISK TO THE SUBJECT, THEN THE RECHALLENGE MUST BE APPROVED IN ADVANCE BY THE LEAD PRINCIPAL INVESTIGATOR AS PER DOSE MODIFICATION GUIDELINES IN THE PROTOCOL.	
	Consistency with Trial Treatment Profile	Is the clinical/pathological presentation of the AE consistent with previous knowledge regarding study agent(s) or drug class pharmacology or toxicology?	
The assessment of elements.	of relationship will	be reported on the case report forms /worksheets by an investigator according to his/her best clinical judgment, including consideration of the above	
Record one of th	ne following	Use the following scale of criteria as guidance (not all criteria must be present to be indicative of study agent(s) relationship).	
Yes, there is a reasonable possibility of study agent(s) relationship.		There is evidence of exposure to study agent(s). The temporal sequence of the AE onset relative to the administration of study agent(s) is reasonable. The AE is more likely explained by study agent(s)than by another cause.	
No, there is not a possibility of stu relationship		Subject did not receive the study agent(s) OR temporal sequence of the AE onset relative to administration of study agent(s) is not reasonable OR the AE is more likely explained by another cause than the study agent(s). (Also entered for a subject with overdose without an associated AE.)	

Protocol Version: 04/10/2019 Page 52 of 72

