If a subject's study treatment has been interrupted for more than 2 doses of pembrolizumab, the investigator must contact the Lead Principal Investigator to review the subject's condition in order to resume the treatment.

If toxicities develop requiring treatment hold of pembrolizumab then EDP1503 supplement should be held as well. If toxicities not characteristic to pembrolizumab are present and the treating investigator believes the patient is deriving clinical benefit, pembrolizumab can be continued while holding EDP1503.

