- Derosa et al 2017. Impact of antibiotics on outcome in patients with metastatic renal cell carcinoma treated with immune checkpoint inhibitors. Poster Abstract 462. J Clin Oncol 35, 2017

Subjects who, in the assessment by the treating investigator, require the use of any of the aforementioned treatments for clinical management should be removed from the trial or in the case of antibiotics the Bifidobacteria components of the study should be temporarily stopped. Subjects may receive other medications that the treating investigator deems to be medically necessary.

The Exclusion Criteria describes other medications which are prohibited in this trial.

There are no prohibited therapies during the Post-Treatment Follow-up Phase.

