8.2.3 Immediate Reporting of Adverse Events to the Principal Investigator and to Merck

8.2.3.1 Serious Adverse Events

A serious adverse event is any adverse event occurring at any dose or during any use of Merck's product that:

- Results in death;
- Is life threatening;
- Results in persistent or significant disability/incapacity;
- Results in or prolongs an existing inpatient hospitalization;
- Is a congenital anomaly/birth defect;
- Is a new cancer (that is not a condition of the study);
- Is associated with an overdose;
- Is an other important medical event

Refer to Table 6 for additional details regarding each of the above criteria.

Any serious adverse event, or follow up to a serious adverse event, including death due to any cause other than progression of the cancer under study that occurs to any subject from first day of study drug administration through 90 days following cessation of treatment, or the initiation of new anti-cancer therapy, whichever is earlier, whether or not related to Merck or Evelo product, must be reported within 24 hours of site knowledge of the event to the UC CCC

Cancer Clinical Trials Office and Lead Principal Investigator and within 2 working days to Merck and Sarah Cannon Development Innovation Safety Department who will hold the Global Safety Database for EDP1503.

Non-serious Events of Clinical Interest will be forwarded to Merck and Sarah Cannon Development Innovation Safety Department and will be handled in the same manner as SAEs.

Additionally, any serious adverse event, considered by an investigator to be related to Merck product that is brought to the attention of the investigator at any time outside of the time period specified in the previous paragraph also must be reported immediately to the UC CCC Cancer Clinical Trials Office and Principal Investigator and to Merck and Evelo.

SAE reports and any other relevant safety information are to be forwarded to the Merck Global Safety [contact] and to Sarah Cannon Development Innovation Safety Department [contact].

All subjects with serious adverse events must be followed up for event outcome.

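### In the combination phase, Table 6 lets an EDP1503-only hold score as a negative dechallenge but never as a positive one, and it asks for only one relationship entry for both agents

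*Combined protocol and SAP*

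**What the plan says.** Table 6 in Section 8.2.4 puts the dechallenge question to the study agents without naming one: "Was study agent(s) discontinued or dose/exposure/frequency reduced". If so, it asks whether the event resolved or improved, and scores the answer: "If yes, this is a positive dechallenge. If no, this is a negative dechallenge". A note then lists cases in which the criterion does not apply. Two of them are tied to pembrolizumab alone: "2) the AE resolved/improved despite continuation of pembrolizumab" and "4) pembrolizumab is only used one time". The rechallenge note repeats the single-use exception, again for pembrolizumab alone. Neither note has matching wording for EDP1503.

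Section 5.2.1.2 provides for stopping one agent without the other. If a toxicity is not characteristic of pembrolizumab and the investigator believes the patient is benefiting, "pembrolizumab can be continued while holding EDP1503". Section 5.5.2 gives a second route: "in the case of antibiotics the Bifidobacteria components of the study should be temporarily stopped".

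The relationship entry in Table 6 is a Yes or a No. The affirmative choice reads "Yes, there is a reasonable possibility of study agent(s) relationship". No section calls for a separate entry for each agent. Section 10.1 plans to tabulate adverse events by type, severity and attribution, without saying attribution to what.

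**The concern.** In a single-agent trial, exception (2) makes sense: if the event cleared while the drug was still being given, nothing was learned from stopping it. With two agents, continuing pembrolizumab says nothing about whether EDP1503 was stopped. An event that clears when EDP1503 alone is withdrawn is direct evidence about EDP1503, the agent under test, and the note sets it aside.

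The single relationship entry adds to this. The trial has no pembrolizumab-only arm, so event-level attribution is one of the few ways to tell the two agents apart once both are being given. A record that does not name the agent makes the planned attribution table less informative for the secondary objective on combination safety (Section 3.2). Other parts of the plan presuppose agent-level judgment. In Section 8.2.3.1, reporting of late serious events turns on relationship to the Merck product. In Section 8.2.3.2, unexpectedness is defined against the particular agent. Section 8.2.3.1 also sends reports to the "Sarah Cannon Development Innovation Safety Department who will hold the Global Safety Database for EDP1503" as well as to Merck.

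**Working it through.** No sample size, error rate or event count is involved, so the check applies the Table 6 rule to each situation that the plan allows.

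**Run-in, EDP1503 only (Section 5.2.2)**
- EDP1503 stopped, event resolves: no pembrolizumab is being continued, so exception (2) cannot apply. Result: positive.
- EDP1503 stopped, event persists. Result: negative.

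**Combination phase, EDP1503 held and pembrolizumab continued (Section 5.2.1.2)**
- Event resolves: the scoring lines call this positive, but exception (2) applies. Result: not applicable.
- Event persists: exception (2) requires resolution or improvement, so it does not apply. Result: negative.

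**Combination phase, both agents held**
- Event resolves. Result: positive, but not assignable to either agent.
- Event persists. Result: negative for both.

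For an EDP1503-only hold in the combination phase, the possible scores are therefore negative or not applicable. Section 5.2.1.2 also says that when toxicity requires a hold of pembrolizumab, EDP1503 should be held too. A toxicity-driven hold that separates the agents is thus an EDP1503-only hold, the one case in which a favourable result is voided.

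**How much EDP1503 exposure falls in the combination phase.** The trial summary gives an average treatment length of 3 months, taken here as about 13 weeks. The run-in is one or two weeks (Section 5.2.2). The summary does not say whether the 3 months include it.
- Lowest share: one-week run-in added to the 13 weeks, 1 / (13 + 1) = 7%.
- Highest share: two-week run-in counted within the 13 weeks, 2 / 13 = 15%.

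On these figures, roughly 85% to 93% of average planned treatment time falls in the phase where exception (2) can apply. This is exposure time. It does not count affected events.

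**Relationship entry.** Table 6 offers one Yes/No for the study agents. Section 10.1 tabulates attribution and specifies no agent. Taken together, they do not require any output that separates EDP1503 from pembrolizumab.

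**The case against.** The strongest reply is that little depends on the dechallenge score. Table 6 presents its criteria as guidance, says that not all need be met, and leaves the entry to the investigator's clinical judgment. The Yes and No definitions rest on exposure, time course and likelier cause; neither mentions dechallenge. Start and stop dates and any resulting discontinuation of study agents are still recorded. An event that cleared on an EDP1503-only hold can still be marked Yes. All of this stands, so it would be wrong to infer that the assessment becomes blind to EDP1503 once pembrolizumab starts. The narrower point remains: one criterion gives a one-sided result for EDP1503, and a Yes need not say which agent is meant.

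The toxicity route is also narrow. It needs a toxicity not characteristic of pembrolizumab and a belief in clinical benefit. Many holds will involve both agents and never meet exception (2).

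A per-agent field may exist on the case report form, which is not in the documents. Part of the relationship row in Table 6 also appears empty in the extracted text. The supportable statement is therefore that the plan does not require separate entries, not that none exist.

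Finally, within the reporting window serious events go to both safety departments whether or not they are related (Sections 8.2.3.1, 8.2.7 and 8.2.8). The documents do not show that any such report would be lost.

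**Conclusion.** The point holds for the combination phase. Exception (2) conflicts with the table's own scoring lines whenever EDP1503 is held alone, and the single relationship entry leaves the planned attribution table free to merge the two agents. The consequence is limited to descriptive safety results for the secondary combination objective. It merits correction but does not put the trial's main conclusions in doubt. The number of affected events cannot be estimated, because the plan gives no rate for EDP1503-only holds or for related events.

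Two stronger readings are tempting and are not supported.
- A reader might infer that the go decisions are compromised, since Section 10.1 makes both conditional on EDP1503 safety. That condition is the co-primary objective, measured as the incidence of adverse and serious adverse events in the run-in. No pembrolizumab is given then, and incidence does not depend on causality.
- A reader might infer from the single-use exception that every dechallenge before the second pembrolizumab dose is void. In the run-in pembrolizumab has not been used at all, so the exception does not apply. After the first dose, its wording fits a patient or trial with a single administration at least as well as a patient awaiting the next one.

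The verdict assumes that Table 6 is applied as worded and that the case report form follows it.

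**What to change.** - In the Table 6 dechallenge and rechallenge notes, replace the references to pembrolizumab with the agent being assessed.
- Record dechallenge, rechallenge and relationship separately for EDP1503 and for pembrolizumab, and confirm that the case report form carries both entries.
- In Section 10.1, state that combination-period adverse events will be tabulated by attribution to each agent.

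Two related inconsistencies can be settled in the same amendment. Section 5.2.1.2 uses graded relatedness (possibly, probably, definitely) where Table 6 allows only Yes or No. Section 4.2.2 and two places in Section 5.5.2 differ on whether EDP1503 is interrupted during antibiotics. Those passages must be reconciled, and this review takes no position on which should stand.

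The cost is wording in Table 6 and Section 10.1, one extra attribution field per adverse event, and slightly more site work. No visits are added, and sample size, endpoints and decision rules do not change. The change is best made early, because agent-level attribution is hard to reconstruct reliably after the event.

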8.2.5 Serious Adverse Event Reporting to the Coordinating Center

All Adverse Events will be reported to regulatory authorities, IRB/IECs and investigators in accordance with all applicable global laws and regulations.

For reporting SUSARs, reporting will comply with CFR 312.32.

All serious adverse events and all Events of Clinical Interest that have been specified to require expedited reporting occurring on this study require expedited reporting to the University of Chicago Comprehensive Cancer Center (UC CCC). The responsible Research Nurse or other designated individual at the treating site should report the SAE to the Lead Principal Investigator and the Cancer Clinical Trials Office (CCTO) within 24 hours of site knowledge of the event. Reports should be made using the 'Serious Event Report' Form. Please scan and send via email (preferred) or fax to the following:

University of Chicago Phase II CRA General: [contact]

[contact] [contact]

UC CCC Cancer Clinical Trials Office Quality Assurance: [contact]

All unexpected adverse reactions must be reported to the IND holder so that the University of Chicago CCTO can inform the FDA. The responsible Research Nurse or other designated individual at the treating site should provide a complete written report using the FDA The completed form should be sent to the CCTO at MedWatch 3500A form. [contact] and to the Phase П CRA at [contact] within the specified timelines below regardless of whether all information regarding the event is available. If applicable, a follow-up report should be provided to the CCTO if additional information on the event becomes available.

Participating sites should not forward any adverse event reports directly to the FDA. The CCTO will report all events to the FDA as per the current FDA guidelines.

Fatal or Life-threatening Events: within 4 calendar days from treating investigator knowledge of the event

All Other Reportable Events: within 10 calendar days of treating investigator knowledge of the event

All serious adverse events should also be reported to the local IRB of record according to their policies and procedures.

Protocol Version: 04/10/2019 Page 53 of 72

